9.6 Safety Analyses

9.6.1 Analyses of Primary Safety Endpoint(s)

Not applicable.

9.6.2 Adverse Events

The Medical Dictionary for Regulatory Activities (MedDRA) version 20.0 or later will be used to code all events categorized as adverse events to a system organ class and a preferred term.

Subject incidence of all treatment-emergent adverse events, serious adverse events, grade 3 and above adverse events, **Treatment-emergent treatment-related** adverse events, **Treatment-emergent treatment-related** serious adverse events, adverse events leading to withdrawal of investigational product or other protocol-required therapies, and fatal adverse events will be tabulated by system organ class and preferred term in alphabetical order.

Subject incidence of events of interest (standardized MedDRA queries and/or Amgen customized queries) will also be summarized according to their categories and preferred term.

In addition, summaries of treatment-emergent adverse events, serious adverse events, grade 3 or higher adverse events, **Treatment-emergent treatment-related** adverse events, **Treatment-emergent treatment-related** serious adverse events, adverse events leading to withdrawal from investigational product or other protocol-required therapies, and fatal adverse event of the subjects by preferred term will be provided in descending order of frequency.

Summaries of treatment-emergent adverse events, **Treatment-emergent treatment-related** adverse events, **Treatment-emergent treatment-related** serious adverse events and serious adverse events will be tabulated by system organ class, preferred term, and grade. Fatal adverse events by system organ class and preferred term will also be provided in descending order of frequency

A summary of the number of deaths and the cause of death, classified by deaths within 30 days of last dose of study drug and deaths more than 30 days after the last dose, will be provided.

9.6.3 Laboratory Test Results

The laboratory test results and their change from baseline will be summarized by cycle.

Actual value and change from baseline of hematology, chemistry, and other laboratory values will be summarized by cycle. For the summary of changes from baseline values, subjects without baseline and/or post baseline values will be excluded. Laboratory assessments collected > 30 days after the last dose will not be included in the summaries.

Selected laboratory test results will be assigned toxicity grades using CTCAE 5. Shift tables assessing the toxicity grade at baseline versus worst toxicity on study and to the last value recorded on study will be presented for selected laboratory test results. A listing of all grade 3 or higher laboratory values will be provided.

The laboratory analytes in the study are given below.

Local Laboratory: Chemistry	Local Laboratory: Hematology	Local Laboratory: Disease Assessments	Other Labs
Sodium	ANC	FISH (bone marrow aspirate)	Central Laboratory: PK (optional)
Potassium	RBC	SPEP	PDn (optional)
Chloride	Hemoglobin	SIFE	PG (optional)
Bicarbonate/CO ₂	Hematocrit	UPEP	Biomarker samples (optional)
Total protein	MCV	UIFE	MRD assessment by NGS (bone marrow aspirate)
Albumin	MCH	SFLC	Local Laboratory: Serum or urine
Calcium	MCHC	Local Laboratory: Urinalysis:	Pregnancy
Adjusted/corrected calcium	RDW	• Specific Gravity	Quantitative immunoglobulins (serum):
Glucose	Platelets	• pH	• IgA, IgD, IgE, IgG, IgM
BUN or Urea	WBC	• Blood	beta2-microglobulin (serum)
Creatinine	Differential	• Glucose	NT-proBNP (or if unavailable, BNP)
Uric acid	*(including manual)	• Ketones	HBV serology
Total bilirubin	• Plasma Cells	• Protein	Hepatitis B DNA
Direct bilirubin	• Bands/stabs	• Bilirubin	
ALP	• Eosinophils	• WBC	
LDH	• Basophils	• RBC	
AST (SGOT)	• Lymphocytes	• Bacteria	
ALT (SGPT)	• Monocytes	• Casts	
Phosphorus	• Segmented Neutrophils	• Crystals	
Amylase			
Lipase	Local Laboratory: Coagulation		
HbA1c			
Fasting glucose (screening)	PT/INR		
Fasting lipid panel:	APTT		
• Cholesterol			
• HDL			
• LDL			
• Triglycerides			

9.6.4 Vital Signs

The vital sign results including systolic/ diastolic blood pressure, heart rate, temperature, and if available, respiratory rate and oxygen saturation and their change from baseline will be summarized by cycle. For the summary of changes from baseline by visit, subjects without a baseline and/or post baseline value will be excluded; values from unscheduled assessments will be excluded. Vital sign results taken > 30 days after the last administration of protocol therapy will be excluded from all vital sign summaries.

9.6.5 Physical Measurements

The physical measurements weight, BSA and their change from baseline will be summarized by cycle. Body surface area (BSA) should be calculated using the Mosteller Formula (Mosteller, 1987):

$$\text{BSA (m}^2\text{)} = ([\text{height (cm)} \times \text{weight (kg)}] / 3600)^{1/2}.$$

9.6.6 Electrocardiogram

The ECG measurements from this clinical study are performed as per standard of care for routine safety monitoring, rather than for purposes of assessment of potential QTc effect. Since these evaluations may not necessarily be performed under the rigorous conditions expected to lead to meaningful evaluation of QTc data; summaries and statistical analyses of ECG measurements are not planned, and these data would not be expected to be useful for meta-analysis with data from other trials.

9.6.7 Antibody Formation

Not Applicable

9.6.8 Exposure to Investigational Product

Descriptive statistics will be produced to describe the exposure to investigational product. The extent of exposure to **investigational products** (carfilzomib and pomalidomide) will be evaluated with respect to treatment duration, number of cycles started, total dose received, average dose received, number of doses administered, and dose intensity. The reasons for dose modification or discontinuation from any study treatment will be summarized. **If the reason for dose modification is COVID-19 control measures which is recorded in the specified field (Other) on the CRF, then the number (%) with COVID-19 control measures will also be presented. The summary will include the following:**

- Number (%) of subjects with doses missed, dose delays, dose reductions, and dose interruptions for carfilzomib will be summarized.
 - Number of doses missed, delayed, reduced, and interrupted per subject
 - Primary reasons for dose missed, delays, reductions, and interruptions.
- Number (%) of subjects with doses missed, dose delays, dose reductions, and dose interruptions for pomalidomide.
 - Number of doses missed, delayed, reduced, and interrupted per subject
 - Primary reasons for dose missed, delays, reductions, and interruptions.

Some variables of interest ie, treatment duration, number of cycles started, total dose received, number of doses administered, and dose intensity are defined in the section 5.

- Number (%) of subjects dosed by cycle for any study drug, each study drug and all study drugs

9.6.9 Exposure to Non-investigational Product

Descriptive statistics will be produced to describe the exposure to non-investigational product. The extent of exposure to non-investigational product (dexamethasone) will be evaluated with respect to treatment duration, number of cycles started, total dose received, average dose received, number of doses administered, and dose intensity. The reasons for dose modification or discontinuation from any study treatment will be summarized. If the reason for dose modification is COVID-19 control measures which is recorded in the specified field (Other) on the CRF, then the number (%) with COVID-19 control measures will also be presented. The summary will include the following:

- **Number (%) of subjects with doses missed, dose delays, dose reductions, and dose interruptions for dexamethasone.**
 - **Number of doses missed, delayed, reduced, and interrupted per subject**
 - **Primary reasons for dose missed, delays, reductions, and interruptions.**

Some variables of interest ie, treatment duration, number of cycles started, total dose received, number of doses administered, and dose intensity are defined in the section 5.

9.6.10 Exposure to Other Protocol-required Therapy

Not applicable.

9.6.11 Exposure to Concomitant Medication

Number and proportion of subjects receiving therapies of interest will be summarized by preferred term for each treatment group as coded by the World Health Organization Drug dictionary.

9.7 Other Analyses

Echocardiogram, including LVEF will be summarized by actual values and changes from baseline values by visit using descriptive statistics.

Pulmonary Function Tests, including spirometry and DLCO, will be summarized by actual values and changes from baseline values by visit using descriptive statistics.

9.7.1 Analyses of Pharmacokinetic or Pharmacokinetic/Pharmacodynamic Endpoints

Carfilzomib PK parameters (maximum observed concentration [C_{max}], area under the concentration-time curve [AUC], and if feasible, terminal half-life [$t_{1/2}$]) will be estimated from plasma concentration-time profiles obtained from subjects enrolled in the optional PK/PDn substudy. Additional analyses may be performed to evaluate relationships between carfilzomib PK and selected safety or efficacy endpoints.

For carfilzomib PDn parameters, proteasome activity for the chymotrypsin-like, trypsin-like and caspase-like activities from whole blood will be reported for the scheduled timepoints to determine if carfilzomib treatment produces a pharmacodynamic reduction in proteasome activity relative to baseline activity levels.

PK/PDn analyses will be provided by the Department of Clinical Pharmacology, Modeling & Simulation (CPMS) (PK analyses) and Clinical Biomarkers and Diagnostics (CBD) (PDn analyses). Details regarding the analyses will be provided in a separate population modeling analysis plan by CPMS and CBD.

9.7.2 Analyses of Clinical Outcome Assessments

Not Applicable

9.7.3 Analyses of Health Economic Endpoints

Not Applicable

9.7.4 Analyses of Biomarker Endpoints

Not Applicable

10. Changes From Protocol-specified Analyses

The Per Protocol Set(s) is added in section 6.3 and it includes subjects who do not have important protocol deviations that might affect the interpretation of the analyses of the efficacy endpoints.

Per the protocol amendment 4 (section 10.2.4), incomplete dates for the start of adverse event, concomitant medications, and death will be imputed and the detailed rules will be specified in the statistical analysis plan.

Addition to the start dates, stop of adverse event, concomitant medications, new antimyeloma therapy, death, prior multiple myeloma therapy, and relapse/progression to prior multiple myeloma therapy will be imputed by the algorithms (section 8.3).

Impact analyses of COVID-19 on the overall trial conduct and assessment of safety and efficacy parameters are added in the statistical analysis plan.

SAP contains some changes in subgroups (section 4.2) from Protocol.

- Added below subgroups for primary endpoint:
 - Cytogenetic risk measured by FISH (high risk (t(4;14), t(14;16), deletion 17p), standard risk)
 - R-ISS (stage I, stage II, stage III)
 - Prior anti-CD38 exposure (yes, no)
 - Refractory to prior anti-CD38 treatment (yes, no)
 - Prior bortezomib exposure (yes, no)
 - Refractory to prior bortezomib treatment (yes, no)
- Added below subgroups for PFS:
 - prior carfilzomib exposure (yes, no)
 - number of prior lines of therapy (1, 2)
 - timing of lenalidomide refractoriness (during maintenance: yes, no)
 - Cytogenetic risk measured by FISH (high risk (t(4;14), t(14;16), deletion 17p), standard risk)
 - R-ISS (stage I, stage II, stage III)
 - Prior anti-CD38 exposure (yes, no)
 - Refractory to prior anti-CD38 treatment (yes, no)
 - Prior bortezomib exposure (yes, no)
 - Refractory to prior bortezomib treatment (yes, no)

11. Literature Citations / References

Klein JP and Moeschberger ML. Survival Analysis: Techniques for Censored and Truncated Data. Springer, 1997.

Appendix A. Handling of Dates, Incomplete Dates and Missing Dates

A1. Imputation Rules for Adverse Events and Concomitant Medications (other than the new anti-myeloma therapy) dates

Imputation Rules for Partial or Missing Start Dates

The reference date for the following rules is the date of first dose.

Start Date		Stop Date						
		Complete: yyyymmdd		Partial: yyyymm		Partial: yyyy		Missing
		< 1st dose	≥ 1st dose	< 1st dose yyyym m	≥ 1st dose yyyy mm	< 1st dose yyyy	≥ 1st dose yyyy	
Partial: yyyym m	= 1st dose yyyymm	2	1	n/a	1	n/a	1	1
	≠ 1st dose yyyymm		2	2	2	2	2	2
Partial: yyyy	= 1st dose yyyy	3	1	3	1	n/a	1	1
	≠ 1st dose yyyy		3		3	3	3	3
Missing		4	1	4	1	4	1	1

1=Impute the date of first dose; 2=Impute the first of the month; 3=Impute January 1 of the year; 4=Impute January 1 of the stop year

Note: For subjects who were never treated (first dose date is missing), partial start dates will be set to the first day of the partial month or first day of year if month is also missing.

Imputation Rules for Partial or Missing Stop Dates

Initial imputation

- If the month and year are present, impute the last day of that month.
- If only the year is present, impute December 31 of that year.
- If the stop date is entirely missing, assume the event or medication is ongoing.
- If the imputed stop date is before the start date, set stop date to missing.

- If the imputed stop date is after the death date, impute as death date.

A2. Imputation Rules for New Antimyeloma Therapy Start Date

If the start day of new antimyeloma therapy is missing and month and year are not the same as last dosing date of study treatment, it will be assumed to be the first day of the month. If the start day of new antimyeloma therapy is missing and month and year are same as last dosing date of study treatment, the start date will be assumed as last dosing date of study treatment. In other situations, do not impute.

A3. Imputation Rules for Partial or Missing Death Dates

If death year and month are available but day is missing:

- If yyyyymm for the date last known to be alive equals yyyyymm for death date, set death date to the day after the date last known to be alive.
- If yyyyymm for the date last known to be alive is less than the yyyyymm for death date, set death date to the first day of the death month.
- If yyyyymm for the date last known to be alive is greater than yyyyymm for death date, assume death date is in error, do not impute and censor the subject survival time.

If month and day are missing and year of death is known:

- If yyyy for the date last known to be alive equals yyyy for death date, set death date to the day after last known to be alive date.
- If yyyy for the date last known to be alive is less than yyyy for death date, set death date to the first day of the death year.
- If yyyy for the date last known to be alive is greater than yyyy for death date, assume death date is in error, do not impute and censor the subject survival time.

If a death date is totally missing:

Do not impute and censor the subject survival time.

A4. Imputation Rules for Dates of Prior Multiple Myeloma Therapy and Relapse/progression to Prior Multiple Myeloma Therapy:

If the day of prior multiple myeloma therapy or relapse/progression to prior multiple myeloma therapy is missing but month and year are available, then impute the date to 15th of the month. If month or year is missing or the date is completely missing, do not impute.

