9.2.4.1 Time Period and Frequency for Collecting and Reporting Safety Event Information

9.2.4.1.1 Adverse Events

The adverse event grading scale to be used for this study will be the Common Terminology Criteria for Adverse Events (CTCAE) version 5 and is described in Section 12.4.

The investigator is responsible for ensuring that all adverse events observed by the investigator or reported by the subject that occur after signing of the informed consent through 30 days after the last dose of study drugs (carfilzomib, pomalidomide, and dexamethasone) are reported using the Events CRF.

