Examples of such events include invasive or malignant cancers, intensive treatment in an emergency room or at home for allergic bronchospasm, blood dyscrasias or convulsions that do not result in hospitalization, or development of drug dependency or drug abuse.

Recording Adverse Events and Serious Adverse Events

Adverse Event and Serious Adverse Event Recording

- When an adverse event or serious adverse event occurs, it is the responsibility of the investigator to review all documentation (eg, hospital progress notes, laboratory, and diagnostics reports) related to the event.
- The investigator will then record all relevant adverse event/serious adverse event information in the Events case report form (CRF).
- The investigator must assign the following adverse event attributes:
 - Adverse event diagnosis or syndrome(s), if known (if not known, signs or symptoms);
 - Dates of onset and resolution (if resolved);
 - Did the event start prior to first dose of investigational product
 - Assessment of seriousness;
 - Severity (or toxicity defined below);
 - Assessment of relatedness to investigational product (carfilzomib and/or pomalidomide), or other protocol-required therapies;
 - Action taken; and
 - Outcome of event
- If the severity of an adverse event changes from the date of onset to the date of resolution, record as a single event with the highest grade (Grades 1 to 4) on the Events CRF. Record a Grade 5 adverse event as a separate event with a 1-day duration.
- It is not acceptable for the investigator to send photocopies of the subject's medical records to Amgen in lieu of completion of the Events CRF page.

- If specifically requested, the investigator may need to provide additional follow-up information, such as discharge summaries, medical records, or extracts from the medical records. In this case, all subject identifiers, with the exception of the subject number, will be blinded on the copies of the medical records before submission to Amgen.
- The investigator will attempt to establish a diagnosis of the event based on signs, symptoms, and/or other clinical information. In such cases, the diagnosis (not the individual signs/symptoms) will be documented as the adverse event/serious adverse event.

Evaluating Adverse Events and Serious Adverse Events

Assessment of Severity

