3. SERIOUS ADVERSE EVENT																															
Provide the date the Investigator became aware of this information: Day Month Year																															
Serious Adverse Event diagnosis or syndrome if diagnosis is unknown, enter signs / symptoms and provide diagnosis, when known, in a follow-up report List one event per line. If event is fatal, enter the cause of death. Entry of "death" is not acceptable, as this is an outcome.	Date Started Day Month Year		Date Ended Day Month Year		Check only if event occurred before first dose of IP Is event serious?  Yes  No	If serious enter Serious Criteria code (see codes below)	Relationship Is there a reasonable possibility that the Event may have been caused by IP or an Amgen device used to administer the IP?				Outcome of Event Resolved Not resolved Fatal Unknown	Check only if event is related to study procedure eg, biopsy																			
							
 
 carfilzomib	pomalidomide	IP/Device	IP/Device	
 
 No/	Yes/	No/	Yes/	No/	Yes/	No/	Yes/	
 
 								
 
						carfilzomib		pomalidomide		IP/Device		IP/Device		No/	Yes/	No/	Yes/	No/	Yes/	No/	Yes/			
carfilzomib		pomalidomide		IP/Device		IP/Device																									
No/	Yes/	No/	Yes/	No/	Yes/	No/	Yes/																								
Serious Criteria: 01 Fatal 03 Required/prolonged hospitalization 05 Congenital anomaly / birth defect 02 Immediately life-threatening 04 Persistent or significant disability /incapacity 06 Other medically important serious event																															
4. Was subject hospitalized or was a hospitalization prolonged due to this event?  No  Yes If yes, please complete all of Section 4																															
Date Admitted Day Month Year				Date Discharged Day Month Year																											
5. Was IP/drug under study administered/taken prior to this event?  No  Yes If yes, please complete all of Section 5																															

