Treatment-emergent adverse event: Events categorized as Adverse Events (AEs) starting on or after first dose of **any study treatment** and up to and including 30 days after the last dose of any study treatments excluding events reported after End of Study date.

Treatment Duration (weeks) for each study drug

Treatment duration (weeks) for carfilzomib, dexamethasone and pomalidomide defined as: (Date of last dose – Date of first dose + 1)/7.

6. Analysis Sets

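### SAP Appendix A1 dates some incompletely dated adverse events to first dose, making them treatment-emergent even where the Events CRF records onset before first dose

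*SAP*

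**What the plan says.** **Collection.** Protocol Section 9.2.4.1.1 requires reporting of adverse events that "occur after signing of the informed consent through 30 days after the last dose of study drugs". Screening may last 28 days from consent to enrollment (Section 9.1.1), and treatment starts within 3 days of enrollment (Section 9.1.2). Pre-dose events are therefore in the database by design.

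**What the investigator records.** Among the attributes that must be assigned to each event, Protocol Section 12.4 lists "Did the event start prior to first dose of investigational product". The paper contingency form for serious events (Figure 12-1) has a matching box: "Check only if event occurred before first dose of IP".

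**Imputation.** In SAP Appendix A1, "The reference date for the following rules is the date of first dose". The start-date grid takes as inputs the recorded parts of the start date, the stop date and the first-dose date. Its codes are "1=Impute the date of first dose; 2=Impute the first of the month", with code 3 giving 1 January of the start year and code 4 giving 1 January of the stop year. For stop dates: "If the stop date is entirely missing, assume the event or medication is ongoing".

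**Classification.** SAP Section 5 reads "Treatment-emergent adverse event: Events categorized as Adverse Events (AEs) starting on or after first dose of" any study treatment, up to 30 days after the last dose. Section 8.3 only refers to Appendix A. Section 9.6.2 lists the tables to be produced and does not mention the CRF item.

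**The concern.** Assigning the first-dose date is a reasonable default when nobody knows whether an event began before or after dosing. Here the trial asks that question for every event. When the answer is Yes, timing relative to first dose is on record, and A1 replaces it with a date that contradicts it. Because the treatment-emergent definition looks only at the date, the contradiction passes straight into the tables.

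Subject incidence of treatment-emergent adverse events is a stated secondary endpoint (SAP Section 2.1), and the treatment-emergent tables in Section 9.6.2 inherit the classification. At stake is whether a myeloma symptom or a screening-procedure event that began before KPd is described as having emerged during it.

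**Working it through.** The plan states no figure on this point, so there is nothing to reproduce. The check reads the A1 grid cell by cell and applies the Section 5 definition to each imputed date.

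**Step 1: where code 1 applies.** These are the three grid rows in which an event could have started on either side of first dose. Cells marked not applicable are left out.

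| Recorded start | Code 1 cells | Applicable cells |
|---|---|---|
| Month and year, same month as first dose | 4 | 5 |
| Year only, same year as first dose | 4 | 6 |
| Missing | 4 | 7 |
| Total | 12 | 18 |

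The other 18 − 12 = 6 cells are those where the stop date itself shows that the event ended before first dose. They receive code 2, 3 or 4, and the event stays pre-treatment. Code 1 also covers a stop date known only to the first-dose month or year, and a missing stop date.

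**Step 2: worked example.** First dose 20 March 2021; recorded start March 2021, day missing; CRF item Yes.

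| Stop date | Imputed start | Treatment-emergent? |
|---|---|---|
| 15 March 2021 | 1 March 2021 | No |
| 25 March 2021 | 20 March 2021 | Yes |
| Missing | 20 March 2021 | Yes |

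In the last two rows the CRF item is the only evidence of earlier onset, and it is not used.

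**Step 3: can a pre-dose onset fall in these rows?** Assume onset is uniform over the 28 days before first dose and first-dose dates are uniform over 2020 and 2021. Then 10,724 of 20,468 day pairs (52%) fall in the first-dose calendar month, and 96% fall in the first-dose year. With the full 28 + 3 = 31 days the shares are 47.5% and 96%. These are shares of possible onset days, not misclassification rates. They show only that, once a date is partial, falling in the same month or year is not unusual.

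**Step 4: effect per subject.** The denominator is the 52 treated subjects (SAP Section 3.2). A subject with no other treatment-emergent event of a given preferred term adds 1/52 = 1.9 percentage points to that term. Three such subjects would add 3/52 = 5.8 points. Three is an illustration; the documents give no count of partial dates.

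**The case against.** **The choice is conservative and has little consequence.** Code 1 can only over-count. The trial has one arm, safety is descriptive, and no test or decision rule uses treatment-emergent incidence. Relatedness is assessed separately (Protocol Section 12.4) and tabulated separately (SAP Section 9.6.2), so a day-1 date says nothing about causality. All of this stands and limits the importance of the point. It does not justify an imputed date that contradicts a recorded answer.

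**The team chose to drop the item.** The SAP's summary of changes says the item was taken out of the treatment-emergent definition by team decision, and the definition now runs from first dose of any study treatment. The item is worded for investigational product, and dexamethasone is not one. A reader might infer that the definition is therefore in error. The documents do not support that: for complete dates a date-only definition is sufficient. Using the item only to guide incomplete dates leaves the definition as it is.

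**Not all partially dated events are affected.** A reader might infer that A1 turns pre-treatment events into treatment-emergent ones in general. It does not. Four things must coincide: onset after consent; a start date that is missing or known only to the first-dose month or year; a stop date not shown to precede first dose; and the item marked Yes. Onset date is itself a required attribute, and nothing in the documents shows that partial dates are common.

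**Worsening events.** An event whose severity changes is recorded once, at its highest grade (Protocol Section 12.4), and Section 5 has no worsening clause. A partially dated screening event that worsens on KPd is now counted through code 1, and using the item would remove it from the tables. This is a real cost, but fully dated pre-dose events that worsen are already left out. The change makes the two consistent, and a listing can keep such events visible.

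**Conclusion.** The point holds in limited form. Where the start is missing or known only to the first-dose month or year, and the stop date does not show that the event ended before first dose, A1 and the Section 5 definition together make the event treatment-emergent whatever the required CRF item says. No other section of the SAP corrects this.

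The error runs one way, towards over-counting, and touches descriptive safety tables only. Its total size cannot be computed from the documents and is probably small. The 1.9 points per subject rests on the denominator of 52 and on the subject having no other treatment-emergent event of that term. The change is worth making because the information is already collected and a stated rule should not override it.

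**What to change.** Add to Appendix A1, for adverse events only:

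> *Where the grid gives code 1 and the CRF item on onset before first dose of investigational product is Yes, impute instead the latest date compatible with the recorded parts that is before first dose of any study treatment. If no such date exists, query the entry and, if unresolved, impute the day before first dose. Apply code 1 only when the item is No or missing.*

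In the example, the last two rows would receive 19 March 2021 and leave the treatment-emergent tables. The query clause is needed when first dose is on the 1st of the month and only that month is recorded, or on 1 January and only that year is recorded. Restricting the sentence to code 1 cells leaves events with a documented pre-dose stop exactly as they are.

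The cost is one sentence and one programming condition on an item already on the Events CRF. There are two downsides:

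- The item refers to investigational product, whereas dexamethasone is given 30 minutes to 4 hours before carfilzomib (Protocol Section 7.1.2.1). An incompletely dated event that began on day 1 after dexamethasone but before the first investigational product could be moved to pre-treatment.
- Partially dated pre-dose events that worsen on treatment would be handled like fully dated ones. List them separately.
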